Itacitinib treatment will continue until treatment failure (cGVHD progression, death, or initiation of new systemic cGVHD therapy), unacceptable toxicity, or withdrawal of consent and for a maximum of 36 months.

[figure not shown]
Part 2 will employ a randomized, double-blind, placebo-controlled design in order to assess the efficacy of itacitinib in combination with corticosteroids using the dose determined to be safe and tolerable in the Part 1 expansion (Figure 1 and Figure 2). Randomization will be stratified by cGVHD risk status (moderate vs severe). Participants randomized to the placebo group will be permitted to cross over to the experimental group after completion of the primary analysis as appropriate. All participants will be followed for survival after completion of study treatment.

Figure 1: Study Design Schema

Note: Treatment Group C discontinued as of SEP 2021.

Figure 2: Treatment Phase, Post-Treatment, and Survival Follow-Up

Adherence to the study design requirements, including those specified in the schedule of activities (Table 4), is essential and required for study conduct.

Table 4: Schedule of Activities

											Follow-Up)	
	Screening					Treatn	nent			Safety	GVHD ^a	Survival	
Visit Day (Range)	Day -28 to -1	D1	1	D14		D28/56/84/ 112/140/168			ЕОТ	Last Dose + 30 days	Q28D/ Q8W°	Q8W From EOT	Notes
Visit Window			±	3 da	ys		±	7 days		+ 5 days	± 7 days	± 14 days	
Administrative procedures	1				ı	1		T		1	r	T	T
Informed consent	X												
Inclusion/exclusion criteria	X												
Demography	X												
Relevant medical history	X												
Prior/concomitant medications	X					X			X	X			
Randomize using IVRS	X												
Contact IVRS/dispense study drug		X				X		X	X				
Administer study drug						X							Hold treatment on clinic visit days until blood draws complete
Administer corticosteroids						X							
Distribute reminder cards						X							
Monitor study drug compliance						X			X				
Monitor corticosteroid use						X			X				
Safety assessments													
AE assessments	X					X			X	X			
Physical exam/vitals/weight	X					X			X	X	X*		*Only weight
KPS	X					X			X	X			
Infection monitoring	X		X*						X*	X*			*As clinically indicated
Graft failure/chimerism*	X ^d					Х*			X*	X*	X*		*As clinically indicated
12-lead ECG	X								X				
Efficacy assessments	Т	1		1		1		T		Т	ı	Γ	T
cGVHD diagnosis and staging	Xe												
cGVHD response		Xf		X		X	X	X	X	Xa	Xa		

Table 4: Schedule of Activities (Continued)

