6.3. Concomitant Medications and Procedures

All concomitant medications and treatments (including over-the-counter or prescription medicines, vitamins, vaccines, and/or herbal supplements) must be recorded in the eCRF. Any prior medication received up to 28 days before the first dose of study treatment and 30 days after the last dose of study treatment, or until the participant begins a new cGVHD therapy, whichever occurs first, will be recorded in the eCRF. Any addition, deletion, or change in the dose of these medications will also be recorded.

Concomitant treatments/procedures that are required to manage a participant's medical condition during the study will also be recorded in the eCRF. The medical monitor should be contacted if there are any questions regarding concomitant or prior therapy.

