8.2.4. Patient-Reported Outcomes

Data from patient-reported changes in health status, symptoms, and well-being will be collected during screening, treatment, and EOT. The following tools will be used to facilitate this collection:

- The LSS consists of 30 items in 7 subscales (skin, eye, mouth, lung, nutrition, energy, and psychological).
- The QOL-SF-36 v2 is 36-item scale that will capture changes in health status during the course of treatment. The SF-36 assesses 8 health concepts related to limitations in physical activities, social activities, bodily pain, general mental and physical health, and vitality.
- The EQ-5D-3L is a descriptive classification consisting of 5 dimensions of health: mobility, self-care, usual activities, anxiety/depression, and pain/discomfort.
- The PGIC is 1 question that will capture the overall change in symptoms over the course of treatment (Appendix F).
- The PGIS is 1 question that will capture the overall change in the severity of symptoms over the previous week (Appendix F).

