8.7. End of Treatment

When the participant permanently discontinues study drug, whether the participant is terminating the study treatment early or has completed the study treatment, the EOT visit should be conducted. If the EOT visit coincides with a regular study visit, the EOT evaluations will supersede those of that scheduled visit, and the data should be entered in the EOT visit in the eCRF. The participant should be encouraged to return for the safety follow-up visit.

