4.2.3. Prior and Concomitant Medication

Prior medication is defined as any nonstudy medication started before the first dose of itacitinib or corticosteroids for participants on corticosteroids only in the Part 1 expansion.

Concomitant medication is defined as any nonstudy medication that is started accordingly:

- Before the date of first administration of itacitinib or corticosteroids only and is ongoing throughout the study or ends on/after the date of first itacitinib or corticosteroid administration.
- On/after the date of first administration of itacitinib or corticosteroids only and is ongoing or ends during the course of itacitinib or corticosteroid treatment.

A prior medication could also be classified as "both prior and concomitant medication" if the end date is on or after the first dose of itacitinib or corticosteroids only. Since corticosteroids are part of the study medication, they will not appear in the list of prior and concomitant medications unless prescribed for an indication other than GVHD. In the listing, it will be indicated whether a medication is prior only, concomitant only, or both prior and concomitant.

For the purposes of analysis, all medications will be considered concomitant medications unless the medications can unequivocally be defined as not concomitant.

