7.3.9. Other Efficacy Analyses

The proportion of participants with $\geq 50\%$ reduction in daily corticosteroid dose at Day 180 will be summarized. Corticosteroid dose on study Day 1 will be defined as the starting dose as appropriate.

The proportion of participants successfully tapered off all corticosteroids at Day 180 will be summarized.

Both time to failure-free survival and average biweekly weight-standardized steroid up to Month 6 will be plotted.

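### Steroid dose and (Part 2) patient-reported outcomes are not scheduled after end of treatment, so Day 180 steroid status may be unknown for participants who stop study drug early without a competing event, and no rule says how to count them.

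*Protocol*

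**What the plan says.** **Collection.** Table 4 marks "Monitor corticosteroid use" in the treatment block and at EOT, and in none of the three follow-up columns. The row "Prior/concomitant medications" extends one column further, to the safety visit, but not into GVHD or survival follow-up. Protocol 8.2.4 says that patient-reported data "will be collected during screening, treatment, and EOT"; Table 4 agrees and limits these instruments to Part 2.

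**What triggers EOT.** Protocol 8.7 ties the EOT visit to one event: "When the participant permanently discontinues study drug". It is therefore not a Day 180 visit for someone who stops early.

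**What follows EOT.** Under Protocol 8.8.2, participants who stop for reasons other than cGVHD progression, and who need no new cGVHD therapy, are seen every 28 days up to one year from Day 1. Table 4 marks cGVHD response, weight, FEV1% and liver chemistry in that column. Protocol 6.3 ends medication recording at "30 days after the last dose of study treatment, or until the participant begins a new cGVHD therapy, whichever occurs first".

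**Endpoints.** A steroid reduction of at least 50% and complete taper-off, both at Day 180, are secondary endpoints in Part 1, the expansion and Part 2. For the second, SAP 7.3.9 says only: "The proportion of participants successfully tapered off all corticosteroids at Day 180 will be summarized". SAP 6.4 names progression, new systemic cGVHD therapy, relapse and death as competing risks. SAP 4.1.5 defers missing data to the endpoint sections.

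**The concern.** The steroid endpoints are fixed-time proportions, but the scheduled steroid record ends when study drug ends. Early stops without a competing event are foreseen. Table 14 shows discontinuation as the first reduction step for Group A participants on a strong CYP3A4 inhibitor, Table 15 lists toxicities that lead to discontinuation, and Protocol 2.3.2.1 reports one itacitinib discontinuation for thrombocytopenia among 21 Part 1 participants. Such a participant may remain on steroids and attend follow-up visits at which nobody is scheduled to record the dose.

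The gap also reaches response. SAP 7.1 counts four situations as new systemic therapy, all wholly or partly defined by steroid changes: new therapy including a dose above Day 1, a second increase, an increase not brought back within six weeks, and reintroduction after a complete taper. SAP 7.3.1 uses new therapy to disqualify Month 3, 6 and 12 responders, and SAP 7.3.3 uses it to end duration of response. An unrecorded steroid change would leave a participant counted as a responder. The four-week steroid summaries in SAP 6.4 and the biweekly steroid plot to Month 6 in SAP 7.3.9 need the same data.

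**Working it through.** The plan states no figure to reproduce. The check sets the schedule against the endpoints and then bounds the effect.

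**1. Sources of steroid information after EOT**
- *Medication recording (Protocol 6.3).* If the window runs from the last itacitinib dose and is taken to cover steroids, a stop on day *s* is covered at Day 180 when *s* + 30 ≥ 180, so *s* ≥ 150. Allowing the 7-day window around the Day 180 visit gives 173 − 30 = Day 143. Earlier stops are not covered, and the window closes sooner if new cGVHD therapy starts.
- *SAP 4.2.3.* Because corticosteroids are study medication, "they will not appear in the list of prior and concomitant medications unless prescribed for an indication other than GVHD". This concerns a list, not collection, but that list will not supply the Day 180 dose.
- *Flare reporting (Protocol 8.2.2).* Steroid changes go on the eCRF when symptoms increase during a taper after an initial response. That does not cover a participant who never responded, or one whose dose is unchanged or falling.
- *New treatment.* Protocol 8.2.2 requires new cGVHD treatment in follow-up to be reported, and 8.8.3 collects subsequent regimens in survival follow-up. Neither gives a steroid dose at a fixed day.

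**2. The rule for counting**
- Stops through progression, new therapy, relapse or death fall under the competing-risk text in SAP 6.4, although it does not say how that text enters a simple Day 180 proportion.
- Stops for tolerability or other reasons have no rule in SAP 6.4 or 7.3.9.
- Response does have one: missing counts as nonresponse (Protocol 10.4.1.2; SAP 7.3.1).

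**3. How many are affected**

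Protocol 2.3.2.3 gives 107 enrolled in the expansion and 62 on treatment at the 09 JUL 2021 cutoff. So 107 − 62 = 45, and 45/107 = 42%, were off treatment. That covers all reasons, all four groups and any duration. The share stopping before Day 180 without a competing event is not given.

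**4. Size under assumed shares**

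With *k* of *n* unknown, the worst-to-best-case width on one group's proportion is *k*/*n*. On a difference between two groups with the same *k*, it is 2*k*/*n*.

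| Assumed share unknown | n = 35: k | One group | Difference | n = 123: k | One group | Difference |
|---|---|---|---|---|---|---|
| 5% | 2 | 5.7 points | 11.4 | 6 | 4.9 points | 9.8 |
| 10% | 4 | 11.4 | 22.9 | 12 | 9.8 | 19.5 |
| 20% | 7 | 20.0 | 40.0 | 25 | 20.3 | 40.7 |

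**5. Effect of a default**

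If true taper-off is 50% and 15% are unknown (both assumed), counting unknowns as not tapered gives 0.50 × (1 − 0.15) = 42.5%. With 10% and 25% unknown it gives 45% and 37.5%.

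**The case against.** The strongest reply is that the steroid record may not end with itacitinib at all. Table 16 lists corticosteroids as study treatment, so the 30-day window can be read as running from the last steroid dose. SAP 6.4 computes steroid duration from the steroid's own first and last dates, and SAP 9.2.3 tabulates steroid discontinuation separately. Protocol 6.1.2.3 has dose changes documented in the medical record and monitored by the sponsor. The CRFs, approved 13 OCT 2021, are not in the documents and may capture more. A reader might infer that early stoppers have no steroid data; these points show that the documents do not support that. What stands is that no steroid or medication entry is scheduled at GVHD follow-up visits, and capture of the Day 180 dose depends on an unsettled reading of the window.

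It can also be said that the affected group is narrow, that these are secondary endpoints with no formal tests in Part 1 or the expansion, and that response is still assessed in follow-up. The first two are fair and limit the severity. The third is only partly right, because SAP 7.1 makes responder status depend on steroid changes.

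Two further inferences are not supported:
- **A Day 180 patient-reported endpoint.** None is defined. The Part 2 endpoint states no timepoint, an EOT value is collected at the stop, and the SAP supplied does not cover Part 2. The point is only that any Day 180 comparison would lack values for early stoppers.
- **A gap confined to the itacitinib groups.** The documents do not say when Group D reaches EOT. If that were when steroids stop, scheduled monitoring would also end there for Group D participants tapered off before Day 180.

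**Conclusion.** The concern holds in a limited form. Steroid use, and Part 2 patient-reported outcomes, have no scheduled collection after EOT, although the participants concerned remain in 28-day clinic follow-up. For those who stop study drug well before Day 180 without a competing event, Day 180 steroid status may be unknown. The steroid-based definition of new systemic therapy can then be applied only from partial flare and subsequent-therapy reporting, and neither SAP 6.4 nor 7.3.9 says how to count these participants.

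The size cannot be read from the documents. The 42% off treatment at the 2021 cutoff is tempting, but it is not the missing fraction. Under an assumed 5% to 20% unknown, one group's proportion is uncertain by about 6 to 20 points with 35 per group, and by a similar amount with 123. The Day 150 threshold assumes that the medication window covers steroids and runs from the last itacitinib dose. No sample-size figure changes. This should be corrected, but it does not threaten the design.

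**What to change.** 1. In Table 4, extend "Monitor corticosteroid use" to the safety and GVHD follow-up columns at least through Day 180, regardless of study-drug status. State in Protocol 6.3 whether the recording window runs from the last itacitinib dose or the last steroid dose.
2. In SAP 6.4 and 7.3.9, state that Day 180 steroid status is taken regardless of itacitinib discontinuation, and that values still missing count as not reduced and not tapered, matching the missing-as-nonresponse rule for response. This default lowers the reported proportion, as step 5 of the working shows, so it should handle what remains after collection and not replace it.
3. In Part 2, collect the patient-reported instruments at the follow-up visit nearest Day 180, and state a timepoint for the endpoint.

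The cost is one extra CRF entry, plus questionnaires in Part 2, at visits already scheduled every 28 days. Table 11 still leaves the Part 2 dose to be determined, so the third change can be made before that part begins.

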	In Part 2, approximately 246 participants will be randomized 1:1 to 1 of 2 treatment groups (123 participants per group).
Study Design	Part 1 and Part 1 expansion: randomized, open-label Part 2: randomized, double-blind, placebo-controlled
Estimated Duration of Study Participation	 It is estimated that an individual participant may participate for as long as 38 months, which includes the following: up to 28 days for screening. continuous treatment until treatment withdrawal criteria are met or for a maximum of 36 months. a minimum of 30 days for safety follow-up. post-treatment cGVHD follow-up for participants who completed itacitinib/placebo taper after initial response (CR or PR) or discontinued early for reasons other than cGVHD progression and with no requirement for new systemic cGVHD therapy (for a maximum of 24 months from Day 1). participants will be followed for survival until the participant dies or withdraws consent.

Treatment Groups and Duration:

Part 1 is a run-in that will employ a randomized, open-label, parallel-cohort design to assess the safety and tolerability of itacitinib in combination with corticosteroids (Figure 1). A total of 20 participants with moderate or severe cGVHD will be randomized 1:1 to itacitinib 200 mg QD plus corticosteroids or 300 mg QD plus corticosteroids.

[figure not shown]
Part 1 expansion is a Phase 2 with an initial safety run-in that will employ a randomized, open-label, parallel-cohort design to assess the safety and preliminary efficacy of itacitinib in combination with corticosteroids compared with corticosteroids monotherapy and select the appropriate dosing/schedule of itacitinib for Part 2 (Figure 2). A total of 140 participants (including those from Part 1) with moderate or severe cGVHD will be randomized 1:1 to 1 of 4 treatment groups that are itacitinib 300 mg QD plus corticosteroids (Treatment Group A), itacitinib 400 mg QD plus corticosteroids (Treatment Group B), itacitinib 300 mg BID plus corticosteroids (Treatment Group C) or corticosteroids monotherapy (Treatment Group D). Treatment Group C was discontinued as of Amendment 8. Randomization will be stratified by

cGVHD risk status (moderate vs severe). Treatment Groups B and C will have an initial safety run-in of 10 participants each to determine safety and tolerability of the dose before expanding.

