											Follow-Up)		
	Screening					Treatm	ent			Safety	GVHD ^a	Survival		
Visit Day (Range)	Day -28 to -1	D1	D7	D14	D21	D28/56/84/ 112/140/168	D180	D196+ (Q28D/Q8W) ^b	ЕОТ	Last Dose + 30 days	Q28D/ Q8W°	Q8W From EOT	Notes	
Visit Window			Ⅎ	± 3 day	ys		± ′	7 days		+ 5 days	±7 days	± 14 days		
FEV1% (from PFTs)	X	Xg				X*	X	X**	X	X	X**		*Day 168 FEV1% may be omitted. **Q8W starting at Day 196 up to 1 year (ie, Days 252, 308, and 364) then Q16 weeks. Day 196 may be omitted.	
Disease/malignancy relapse	X							X*					*As clinically indicated.	
LSS		Xh				X	X	X	X				Part 2 only.	
QOL-SF-36 v2		Xh				X*	X	X**	X				Part 2 only.	
EQ-5D-3L		X^h				X*	X	X**	X				* Day 168 may be omitted.	
PGIC						X*	X	X**	X				**Day 196 may be omitted.	
PGIS		Xh				X*	X	X**	X					
New cGVHD therapy data												X		
Survival assessment												X		
Laboratory assessments														
Hematology	X	X^h	X	X	X	X	X	Q28D	X	X				
Serum chemistry	X	X ^h	X	X	X	X	X*	Q28D	X	X	X*		*Total bilirubin, ALT, and ALP. Direct and indirect bilirubin also required for participants with elevated total bilirubin.	
Lipid panel	X	X^h	X	X	X	X		X	X	X				
Serum pregnancy testing	X								X					
Serum or urine pregnancy testing						X		X						
Hepatitis screening	X													
HIV screening	X													
PK sampling (Part 1 and Part 1 expansion)		X	X			X							D1/7/28 only (predose, 1, 2, 5 h) *Treatment Group D in Part 1 expansion does not require PK sampling.	

Table 4: Schedule of Activities (Continued)

											Follow-Up	l	
	Screening					Treatm	ent			Safety	GVHD ^a	Survival	
Visit Day (Range)	Day -28 to -1	D1	D 7	D14	D21	D28/56/84/ 112/140/168	D180	D196+ (Q28D/Q8W) ^b	ЕОТ	Last Dose + 30 days	Q28D/ Q8W°	Q8W From EOT	Notes
Visit Window			±	3 day	ys	± 7 days				+ 5 days	±7 days	± 14 days	
PK sampling (Part 2)		X	X			Х							Participant 1-70: D1/7/28 (predose, 1, 2, 5 h). Participant 71-246: D7/28 (predose only).

VV-CLIN-000629 CONFIDENTIAL

^a Only for participants who completed itacitinib/placebo taper after an initial response (CR or PR) or discontinue early for reasons other than cGVHD disease progression and with no requirement for new cGVHD therapy (for a maximum of 24 months from Day 1).

b Every 28 days (± 7 days) up to 1 year (D364) from Day 1 and then every8 weeks (± 7 days), with the exception of hematology and serum chemistry, which will be performed every 28 days during the entire treatment period.

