8.3.8. Laboratory Assessments

Blood draws for laboratory assessments will occur at study visits indicated in Table 4. Table 21 summarizes the clinical laboratory analytes to be assessed. Blood draws will be completed before the participant receives study drug.

All laboratory assessments will be performed at a local (site) laboratory using institutional best practices. Results and normal reference ranges will be entered into the eCRF.

Table 21: Clinical Laboratory Analytes

Serum Chemistries	Hematology	Pregnancy Testing
Albumin ALP ALT AST Bicarbonate or CO ₂ (at screening and then as clinically indicated) Blood urea nitrogen or urea Calcium Chloride Creatinine Glucose Lactate dehydrogenase Phosphate Potassium Sodium Total bilirubin (Direct and indirect bilirubin required for participants with elevated total bilirubin). Total protein Total cholesterol	Complete blood count, including: Hemoglobin Hematocrit Platelet count Red blood cell count White blood cell count Differential count, including: Basophils Eosinophils Lymphocytes Monocytes Neutrophils	Female participants of childbearing potential only require a serum test at screening and EOT and a serum or urine pregnancy every 28 days. Pregnancy tests (serum or urine) should be repeated if required by local regulations.
Lipid Panel	Infection Screening Tests	
Triglycerides Cholesterol LDL HDL	HIV (if HIV status is unknown) Hepatitis B surface antigen Hepatitis B surface antibody Hepatitis B core antibody HCV antibody HBV-DNA (if required) HCV-RNA (if required) CMV-PCR and EBV-PCR	

Note: Additional tests may be required, as agreed upon by the investigator and sponsor, based on emerging safety data.

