8.3.8.3. Pregnancy Testing

A serum pregnancy test will be required for all women of childbearing potential during screening and at the EOT visit.

Urine or serum pregnancy tests will be conducted locally every 28 days. If a urine pregnancy test is positive, results should be confirmed with a serum pregnancy test. If the serum pregnancy test is negative after a urine test was positive, the investigator will assess the potential benefit/risk to the participant and determine whether it is in the participant's best interest to resume study drug and continue participation in the study.

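### After Day 364, Table 4 puts pregnancy testing on an 8-week cycle, while Section 8.3.8.3 and Table 21 require it every 28 days

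*Protocol*

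**What the plan says.** Three places in the current Protocol set the interval for pregnancy testing during treatment.

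- **Table 4 and footnote b (Section 1).** The row "Serum or urine pregnancy testing" has a plain X under the Day 28 to 168 visits and another under the D196+ (Q28D/Q8W) column, which carries footnote b. That footnote moves the column from 28-day to 8-week visits after Day 364 and names only two assessments that keep the shorter interval: "with the exception of hematology and serum chemistry, which will be performed every 28 days during the entire treatment period". The hematology and serum chemistry rows show Q28D in that column; the pregnancy row does not.
- **Section 8.3.8.3.** "Urine or serum pregnancy tests will be conducted locally every 28 days". No end date or change of interval is given. The section also states: "A serum pregnancy test will be required for all women of childbearing potential during screening and at the EOT visit".
- **Table 21 (Section 8.3.8).** Women of childbearing potential "require a serum test at screening and EOT and a serum or urine pregnancy every 28 days".

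The treatment period is long enough for the difference to matter. Table 3 allows "continuous treatment until treatment withdrawal criteria are met or for a maximum of 36 months".

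**The concern.** Followed as written, the schedule gives an 8-week interval from the second year, and the body text gives 28 days. A site cannot satisfy both. One that works from Table 4 misses about every other test required by Section 8.3.8.3; one that works from Section 8.3.8.3 performs tests the schedule does not list. The paragraph introducing Table 4 makes adherence to it mandatory, and nothing in the Protocol says the body text prevails in a conflict.

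What is at stake is participant safety. Section 9.7 requires a pregnant participant to stop study drug at once, and Section 7.1.1 makes pregnancy a mandatory reason for withdrawal from treatment. Both rules act only after the pregnancy has been detected. Contraception is not a complete safeguard: Appendix A warns that the study drug may interact with hormonal methods and reduce their effectiveness.

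**Working it through.** The documents state no number of tests, so there is no planned figure to reproduce. The check counts the scheduled tests under each reading.

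**Inputs**

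- Start of divergence: Day 364 (Table 4, footnote b).
- End of treatment: at most 36 months (Table 3), taken as about Day 1095.
- Interval under Section 8.3.8.3 and Table 21: 28 days.
- Interval under footnote b after Day 364: 8 weeks = 56 days.
- Visit window: ±7 days (Table 4).

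**Is the X really in the footnoted column?** Yes. The pregnancy row's two marks fall in the same column positions as those of the lipid panel for Days 28 to 168 and D196+. Hematology and chemistry carry Q28D there instead. The table therefore separates rows that stay at 28 days from rows that follow footnote b, and pregnancy testing is in the second group.

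**Number of tests from Day 364 to Month 36**

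- Days available: 1095 − 364 = 731.
- At 28-day spacing: 731 / 28 = 26.1, so 26 tests.
- At 56-day spacing: 731 / 56 = 13.1, so 13 tests.
- Ratio: 13 / 26 = 0.50.

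The counts are the same if Month 36 is placed at Day 1092, 1095 or 1096.

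**Interval between consecutive tests**

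| | 8.3.8.3 and Table 21 | Table 4, footnote b |
|---|---|---|
| Nominal | 28 days | 56 days |
| Longest with windows (first visit 7 days early, next 7 days late) | 28 + 14 = 42 days | 56 + 14 = 70 days |

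The nominal interval doubles. At the extremes of the windows the ratio is 70 / 42 = 1.67. The serum test at end of treatment is required under both readings and is left out of the counts.

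**The case against.** The strongest reply is that footnote b never mentions pregnancy testing. The 8-week interval is inferred from a column heading and an exception list, against two explicit statements of 28 days. The Amendment 6 summary names the assessments whose frequency was reduced, and pregnancy testing is not among them, so the likeliest explanation is an omission from the footnote with 28 days still intended. That is a fair account of how the conflict arose. It does not resolve it, because Table 4 is the schedule sites are told they must follow.

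The second reply concerns size. The count of 26 against 13 is a ceiling: it applies to a woman of childbearing potential who remains on treatment to Month 36 at a site that follows Table 4. Progression, hematologic relapse or a taper will end treatment sooner for many. The doubling is of the nominal interval; with windows the comparison is 42 against 70 days. All of this stands.

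The third reply is mitigation. Eligibility requires contraception with at least 99% certainty, Table 21 asks for repeat tests where local regulations demand them, and a serum test is done at end of treatment. These reduce the risk, and local rules may close the gap at some sites, but none sets a common interval after Day 364.

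**Conclusion.** The inconsistency is real and should be corrected. For a woman treated to Month 36, following Table 4 yields 13 tests after Day 364 instead of the 26 that the body text requires. This rests on reading the plain X with its column footnote, on Month 36 falling at about Day 1095, and on the participant staying on treatment throughout. The number of women affected cannot be estimated from the documents. It is a conflict between passages rather than evidence that the sponsor chose 8-week testing. It bears on safety monitoring only: no endpoint, efficacy analysis or error rate depends on it.

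**What to change.** Add pregnancy testing for women of childbearing potential to the exception in footnote b, beside hematology and serum chemistry, and enter Q28D in the D196+ cell of that row. Section 8.3.8.3 and Table 21 then need no change.

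The cost is a few words, plus 26 − 13 = 13 more local urine or serum tests than Table 4 now schedules for each woman treated to Month 36. The body text already requires those tests, and blood is already drawn every 28 days for hematology and chemistry, so no new visit is needed. If the sponsor does intend 8-week testing after the first year, Section 8.3.8.3 and Table 21 should say so and give the reason.
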